### **3.3.5 Replacement of subjects**

In case some subjects do not complete the trial, the CTL together with the trial pharmacokineticist and the trial statistician are to decide if and how many subjects will be

Proprietary confidential information © 2018 Boehringer Ingelheim International GmbH or one or more of its affiliated companies

replaced. A replacement subject will be assigned a unique trial subject number, and will be assigned to the same treatment as the subject he replaces.

## **4. TREATMENTS**

### **4.1 INVESTIGATIONAL TREATMENTS**

The investigational products have been manufactured by BI Pharma GmbH & Co. KG.

#### **4.1.1 Identity of the Investigational Medicinal Products**

The characteristics of the test product are given below:

Table 4.1.1: 1 Test product

Substance	BI 730357
Pharmaceutical formulation:	Film-coated tablet
Source:	BI Pharma GmbH & Co. KG, Germany
Unit strength:	50 mg (DG 1) or 100 mg (DG 2, DG 3)
Posology:	1-0-0 (DG 1); 1-0-0 (DG 2); 2-0-0 (DG 3)
Route of administration:	oral
Duration of use:	Day 1 (single dose)

DG: dose group

Table 4.1.1: 2 Reference product

Substance	Placebo matching in size and weight to 50 or 100 mg film-coated tablet
Pharmaceutical formulation:	Film-coated tablet
Source:	Boehringer Ingelheim Pharma GmbH & Co. KG, Germany
Unit strength:	n.a.
Posology:	1-0-0 (DG 1) (matching in size and weight to 50 mg film-coated tablet) 1-0-0 (DG 2) (matching in size and weight to 100 mg film-coated tablet) 2-0-0 (DG 3) (matching in size and weight to 100 mg film-coated tablet)
Route of administration:	oral
Duration of use:	Day 1 (single dose)

DG: dose group

#### **4.1.2 Selection of doses in the trial**

Three dose groups are to be investigated in this trial. Three dose levels will cover potential therapeutic dose ranges. The number of dose levels will also allow for evaluation of dose proportionality.

This trial is designed to evaluate the safety, tolerability, and pharmacokinetics of BI 730357 in Japanese healthy male volunteers. A safe and tolerable dose achieved in previous trials, including Caucasian SRD trial (1407.1), is used as a reference for the dose selection in this trial.

For safety margins and further details on dose selection, refer to Section [1.2](#) and [1.3](#).

#### **4.1.3 Method of assigning subjects to treatment groups**

Prior to the screening visit, subjects will be contacted in writing and informed about the planned visit dates. The subjects willing to participate will be recruited to dose groups according to their temporal availability. Therefore, the allocation of subjects to dose cohorts is not influenced by trial personnel, but only by the subjects' temporal availability. As the

Proprietary confidential information © 2018 Boehringer Ingelheim International GmbH or one or more of its affiliated companies

study includes healthy subjects from a homogenous population, relevant imbalances between the dose groups are not expected.

Subjects will be assigned to treatments (active treatment or placebo) prior to the first administration of trial medication. For this purpose, the randomisation list will be provided to the trial site in advance. Subjects are then assigned to treatment according to the randomisation list.

The randomisation procedure is described in Section [7.6](#).

#### **4.1.4 Drug assignment and administration of doses for each subject**

The treatments to be evaluated are outlined in Table 4.1.4: 1 below. The number of units for placebo corresponds to the number of units of the respective dose level.

Table 4.1.4: 1 BI 730357 and placebo treatments, oral administration

Dose group	Substance	Pharmaceutical form	Unit strength	Number of units per administration	Total daily dose
1	BI 730357	film-coated tablet	50 mg	1 tablet	50 mg
2	BI 730357	film-coated tablet	100 mg	1 tablet	100 mg
3	BI 730357	film-coated tablet	100 mg	2 tablet	200 mg
1	Placebo*	Film-coated tablet	--	identical to active treatment	--
2	Placebo*	Film-coated tablet	--	identical to active treatment	--
3	Placebo*	Film-coated tablet	--	identical to active treatment	--

\* Subjects receiving placebo are equally distributed across dose groups

The trial medication will be administered to the subjects, while in a sitting position, as an oral dose together with approximately 240 mL of water, under supervision of the investigating physician or an authorised designee. The so-called four-eye principle (two-person rule) should be applied for administration of trial medication, if correct dosage cannot be ensured otherwise.

Subjects will be kept under close medical surveillance until at least 48 hours following drug administration. During the first 4 hours after drug administration, they are not allowed to lie down (i.e., no declination of the upper body of more than 45 degrees from upright posture), except, if required for trial-related measurements (e.g., recording of 12-lead ECG) or for medical reasons (e.g., AEs).

For restrictions with regard to diet, refer to Section [4.2.2.2](#).

#### **4.1.5 Blinding and procedures for unblinding**

##### **4.1.5.1 Blinding**

The trial is designed double-blind. The treatments administered (active or placebo) will be blinded to the subjects and the investigators (outcome assessors) in order to limit the occurrence of any bias which the knowledge of treatment may have. According to the rising dose design, the current dose level will be known to subjects and investigators.

Proprietary confidential information © 2018 Boehringer Ingelheim International GmbH or one or more of its affiliated companies

At the sponsor's site, access to the randomisation schedule is restricted to the randomisation operators, the Clinical Trial Support group and the Pharmaceutics Department.

The trial pharmacokineticist may receive the randomisation codes prior to official unblinding to perform the preliminary PK analysis. He or she will confirm in writing that the codes will be treated confidentially.

In addition, regarding the sponsor, all trial data will be handled open label. This means that trial functions of the sponsor are unblinded (trial clinical leader, data manager, statistician, bioanalyst, pharmacokineticist as well as dedicated CRO personnel). This is acceptable because they are neither in contact with subjects nor with site staff.

Within the central ECG lab, the staff involved with interval measurements and morphological analyses will be blinded with respect to the treatment and also with regard to the recording date and time as well as planned time points of the ECGs. The interval measurements for a given subject will be performed in a random and blinded sequence by a single technician.

Access to the randomisation schedule will be controlled and documented by a signed confidentiality statement, which will be stored in the TMF.

#### **4.1.5.2 Unblinding and breaking the code**

The investigator or designee will be supplied with a set of sealed envelopes containing the medication codes for each subject according to the randomisation scheme. The envelopes will be kept unopened at the trial site until the end of data collection. An envelope may only be opened in emergency situations when the identity of the trial drug must be known to the investigator in order to provide appropriate medical treatment or otherwise assure safety of trial participants. If the envelope for a subject is opened, the sponsor must be informed immediately. The reason for breaking the code must be documented on the envelope and/or appropriate CRF page along with the date and the initials of the person who broke the code.

PK samples will be labelled in such a way that treatment allocation cannot be derived by the analytical site.

#### **4.1.6 Packaging, labelling, and re-supply**

The investigational medicinal products will be provided by BI. They will be packaged and labelled in accordance with local law and the principles of Good Manufacturing Practice.

For details of packing and the description of the label, refer to the ISF.

No re-supply is planned.

#### **4.1.7 Storage conditions**

Drug supplies will be kept in their original packaging and in a secure limited access storage area according to the recommended (labelled) storage conditions. Where necessary, a temperature log must be maintained to make certain that the drug supplies are stored at the correct temperature. If the storage conditions are found to be outside the specified range, the local clinical monitor (as provided in the list of contacts) is to be contacted immediately.

#### **4.1.8 Drug accountability**

The investigator/pharmacist who is documented in the trial staff list/investigational drug storage manager will receive the investigational drugs delivered by the sponsor when the following requirements are fulfilled:

- Approval of the trial protocol by the institutional review board (IRB),
- Availability of a signed and dated clinical trial contract between the sponsor and the head of the trial site,
- Notification of the regulatory authority, e.g., competent authority (CA)
- Availability of the curriculum vitae of the principal investigator
- Availability of a signed and dated CTP

Only authorised personnel as documented in the form 'Trial Staff List' may dispense medication to trial subjects. The trial medication must be administered in the manner specified in the CTP. All unused medication must be returned to sponsor. Receipt, usage and return must be documented on the respective forms. Account must be given for any discrepancies.

The investigator/pharmacist who is documented in the trial staff list/investigational drug storage manager must maintain records of the product's delivery to the trial site, the inventory at the site, the use by each subject, and the return to the sponsor of unused products.

These records will include dates, quantities, batch/serial numbers, expiry ('use-by') dates, and the unique code numbers assigned to the investigational products and trial subjects. The investigator/pharmacist that is documented in the trial staff list/investigational drug storage manager will maintain records that document adequately that the subjects were provided the doses specified by the CTP, and that reconcile all investigational products received from the sponsor. At the time of return to the sponsor or appointed contract research organization (CRO), the investigator/pharmacist who is documented in the trial staff list/investigational drug storage manager must verify that no remaining supplies are in the investigator's possession.

#### **4.2 OTHER TREATMENTS, EMERGENCY PROCEDURES, RESTRICTIONS**

##### **4.2.1 Other treatments and emergency procedures**

There are no special emergency procedures to be followed. No additional treatment is planned. However, in case of AEs in need of treatment, the investigator can authorise symptomatic therapy. In those cases, subjects will be treated as necessary and, if required, kept under supervision at the trial site or transferred to a hospital until all medical evaluation results have returned to an acceptable level.

#### **4.2.2      Restrictions**

##### **4.2.2.1    Restrictions regarding concomitant treatment**

In principle, no concomitant therapy is allowed. All concomitant or rescue therapies will be recorded (including time of intake on study days) on the appropriate pages of the CRF.

##### **4.2.2.2    Restrictions on diet and life style**

While admitted to the trial site the subjects are restricted from consuming any other foods or drinks than those provided by the staff. Standardised meals will be served at the time points described in the [Flow Chart](#). No food is allowed for at least 4 hours after drug intake.

From 1 hour before drug intake until 4 hours post-dose liquid intake is restricted to the fluid (approximately 240 mL of water) administered with the drug and an additional approximately 240 mL of water served on Day 1 at 2 hours and 4 hours post-dose (mandatory for all subjects).

From 4 hours post-dose until 24 hours post-dose water intake is restricted to 3000 mL. During the days of urine collection, total fluid intake should be at least 1500 mL and should not exceed 3500 mL.

Alcoholic beverages, grapefruits, Seville oranges (sour or bitter oranges) and their juices, and dietary supplements and products including St. John's wort (*Hypericum perforatum*) are not permitted starting 7 days before administration of trial medication until after the last PK sample of each study period is collected.

Smoking is not allowed during in-house confinement at the trial site.

Methylxanthine-containing drinks or foods (such as coffee, tea, cola, energy drinks, and chocolate) are not allowed from 24 hours before administration of trial medication until the end of plasma pharmacokinetic sampling of the respective visit.

Excessive physical activity (such as competitive sport) should be avoided starting 7 days before the first administration of trial medication until the end of study examination.

Direct exposure to the sun or exposure to solarium radiation should be avoided during the entire study.

#### **4.3            TREATMENT COMPLIANCE**

Compliance will be assured by administration of all trial medication in the study centre under supervision of the investigating physician or a designee. The measured plasma concentrations will provide additional confirmation of compliance.

Subjects who are non-compliant (for instance, who do not appear for scheduled visits or violate trial restrictions) may be removed from the trial and the CRF will be completed accordingly (for further procedures, please refer to Section [3.3.4.1](#)).

## **5. ASSESSMENTS**

### **5.1 ASSESSMENT OF EFFICACY**

Not applicable. No efficacy endpoints will be evaluated in this trial.

### **5.2 ASSESSMENT OF SAFETY**

#### **5.2.1 Physical examination**

At screening, the medical examination will include demographics including height and body weight, smoking and alcohol history, relevant medical history and concomitant therapy, review of inclusion and exclusion criteria, review of vital signs (BP, PR, RR, and body temperature), 12-lead ECG, laboratory tests, and a physical examination. At the end of study examination, it will include review of vital signs, 12-lead ECG, laboratory tests, and a physical examination.

#### **5.2.2 Vital signs**

Systolic and diastolic BP as well as PR will be measured by a BP monitor at the times indicated in the [Flow Chart](#), after subjects have rested for at least 10 minutes in a supine position. All recordings should be made using the same type of BP recording instrument on the same arm if possible.

Further, RR and body temperature will be monitored. Body temperature will be determined at the time points indicated in the [Flow Chart](#) using electronic thermometers. RR will be counted by trained study personal by observing the chest movements over a period of one minute (30 second x 2) after the subject has rested in the supine position for 10 minutes. Recording of the values will be done at the time points indicated in the [Flow Chart](#).

#### **5.2.3 Safety laboratory parameters**

For the assessment of laboratory parameters, blood and urine samples will be collected by the trial site at the time points indicated in the [Flow Chart](#) after the subjects have fasted for at least 10 hours. Overnight fasting is not required at the discretion of the investigator or designee for retests.

The parameters that will be determined are listed in Tables [5.2.3: 1](#) and [5.2.3: 2](#). Reference ranges will be provided in the ISF.

Manual differential white blood cell count will only be performed if there is an abnormality in the automatic blood cell count, i.e. if automatic count is not feasible or differential WBC is abnormal (i.e., pathological or atypical cells) and clinically relevant in the opinion of the investigator.

In case the urinalysis is positive for erythrocytes, leukocytes, nitrite or protein and clinically relevant in the opinion of the investigator, microscopic examination of the urine sediment

Proprietary confidential information © 2018 Boehringer Ingelheim International GmbH or one or more of its affiliated companies

will be performed. Positive findings of the urine sediment examination will be monitored and if needed based on the medical judgment of the investigator an urologist may be consulted.

**Table 5.2.3: 1** Routine laboratory tests

Functional lab group	Test name	SCR	A 	B 	EOS 
Haematology	Haematocrit	x	x	x	x
	Haemoglobin	x	x	x	x
	Red blood cell count (RBC)	x	x	x	x
	Reticulocyte count	x	x	x	x
	White blood cell count (WBC)	x	x	x	x
	Platelet count	x	x	x	x
Automatic WBC differential (relative)	Neutrophils, eosinophils, basophils, monocytes, lymphocytes	x	x	x	x
Manual differential WBC (if automatic count is not feasible or differential WBC is abnormal and clinically relevant in the opinion of the investigator)	Polymorphnuclear neutrophils (segs), band neutrophils (stabs), eosinophils, basophils, monocytes, lymphocytes				
Coagulation	Activated partial thromboplastin time (aPTT)	x	x	x	x
	Prothrombin time (Quick's test and INR)	x	x	x	x
	Fibrinogen	x	x	x	x
Enzymes	Aspartate transaminase (AST/GOT)	x	x	x	x
	Alanine transaminase (ALT/GPT)	x	x	x	x
	Alkaline phosphatase (AP)	x	x	x	x
	Gamma-glutamyl transferase (GGT/γ-GT)	x	x	x	x
	Creatine kinase (CK)	x	x	x	x
	CK-MB, only if CK is elevated	x	x	x	x
	Lactate dehydrogenase (LDH)	x	x	x	x
	Lipase	x	x	x	x
	Amylase	x	x	x	x
Hormones	Thyroid stimulating hormone (TSH)	x	--	--	--
Substrates	Plasma glucose	x	x	x	x
	Creatinine	x	x	x	x
	Blood Urea Nitrogen (BUN)	x	x	x	x
	Total bilirubin	x	x	x	x
	Direct bilirubin	x	x	x	x
	Total protein	x	x	x	x
	Albumin	x	x	x	x
	C-Reactive Protein (CRP)	x	x	x	x
	Uric acid	x	x	x	x
	Total cholesterol	x	x	x	x
	Triglycerides	x	x	x	x
Electrolytes	Sodium	x	x	x	x
	Potassium	x	x	x	x
	Calcium	x	x	x	x

Table 5.2.3: 1 Routine laboratory tests (cont).

Functional lab group	Test name	SCR	A 	B 	EOS
Urinalysis (strip of dipstick)	Urine nitrite	x	x	--	x
	Urine protein	x	x	--	x
	Urine glucose	x	x	--	x
	Urine ketone	x	x	--	x
	Urobilinogen	x	x	--	x
	Urine bilirubin	x	x	--	x
	Urine erythrocytes	x	x	--	x
	Urine leukocytes	x	x	--	x
	Urine pH	x	x	--	x
Urine sediment 	Only positive findings will be reported (for instance, the presence of sediment bacteria, casts in sediment, squamous epithelial cells, erythrocytes, leukocytes)	x	x	--	x

SCR: screening, EOS: end of study

1 A: parameters to be determined at Visit 2 on Day -3 to -1, Day 1, 2, 8 (for time points refer to [Flow Chart](#))

2 B: parameters to be determined at Visit 2, after 4 hours on Day 1 (for time points refer to [Flow Chart](#))

3 Only if erythrocytes, leukocytes nitrite or protein are abnormal in urine and are deemed clinically necessary by the investigator

The tests listed in Table 5.2.3: 2 are exclusionary laboratory tests which may be repeated as required. The results will not be entered in the CRF/database and will not be reported in the CTR. Infection serology test will be planned during screening only. Drug screening and alcohol test will be performed at screening and prior to treatment period.

Proprietary confidential information © 2018 Boehringer Ingelheim International GmbH or one or more of its affiliated companies

Table 5.2.3: 2      Exclusionary laboratory tests

Functional lab group	Test name
Drug screening (urine)	Amphetamine/MDA Barbiturates Benzodiazepine Cannabis Cocaine Methadone Methamphetamines/MDMA/XTC Opiates (Morphine) Phencyclidine Tricyclic antidepressants
Infectious serology (blood)	Hepatitis A antibodies (qualitative) Hepatitis B surface antigen (qualitative)  Hepatitis B surface antibody (qualitative)  Hepatitis B core antibody (qualitative)  Hepatitis C antibodies (qualitative) HIV-1 and HIV-2 antigen and/or antibody (qualitative) QuantiFERON TB-Gold or T-SPOT  Syphilis test (RPR, TP antibody method)

Alcohol test

Breath alcohol test

1 If hepatitis B surface antigen and/or hepatitis B core antibody is positive, subject will be not allowed participating in this study. If hepatitis B surface antibody is positive, hepatitis B surface antigen and hepatitis B core antibody is negative, and there is evidence that subject gets hepatitis B virus vaccine, subject will be allowed participating in this study.

2 If QuantiFERON® or T-SPOT® is positive; subject will be not allowed participating in this study. Subject with latent tuberculosis will be not allowed participating in this study.

To encourage compliance with alcoholic restrictions, a breath alcohol test will be performed at screening and prior to each treatment period, and may be repeated at any time during the study at the discretion of an investigator or designee. The results will not be included in the CTR.

The laboratory tests listed in Table [5.2.3: 1](#) and [5.2.3: 2](#) will be performed by the local laboratory at the trial site and/or at an external vendor designated by the site.

Laboratory data will be transmitted electronically from the trial site to BI.

## **5.2.4      Electrocardiogram**

### **5.2.4.1      12-lead resting ECG**

#### Recording

Twelve-lead resting ECGs (I, II, III, aVR, aVL, aVF, V1 - V6) will be recorded using a computerised electrocardiograph (MAC 800 ECG machines, GE Healthcare) at the time points given in the [Flow Chart](#).

Electrode placement will be performed according to the method of Wilson, Goldberger and Einthoven modified by Mason and Likar (hips and shoulders instead of ankles and wrists). Precise electrode placement will be marked with an indelible mark on the skin to allow reproducible placement throughout the study.

Proprietary confidential information © 2018 Boehringer Ingelheim International GmbH or one or more of its affiliated companies

To achieve a stable heart rate (HR) at rest and to assure high quality recordings, the site personnel will be instructed to assure a relaxed and quiet environment so that all subjects are at complete rest.

All ECGs will be recorded for 10-second duration after the subjects have rested for at least 10 minutes in a supine position. ECG recordings will always precede all other study procedures scheduled for the same time point (except blood drawing from an intravenous cannula which is already in place) to avoid impact of sampling on the ECG quality.

ECGs will be recorded as single ECGs or as triplicate ECGs (i.e., three single ECGs recorded within 180 second) as indicated in the [Flow Chart](#).

ECGs may be repeated for quality reasons for instance due to alternating current artefacts, muscle movements, or electrode dislocation. For time points with triple ECGs, all three single ECGs will be repeated. The repeat ECGs are assigned to the respective scheduled time point.

Additional (unscheduled) ECGs may be collected at the discretion of the investigator for safety reasons. These ECGs are assigned to the prior scheduled time point.

#### Storing

All ECGs will be stored electronically on the Muse Cardiology information System (GE Medical Systems, Freiburg, Germany)

#### Data transfer

For time points specified in the [Flow Chart](#), ECGs will be transferred electronically to the central ECG lab ( ) for evaluation.

All ECGs (including repeat ECGs due to quality reasons) will be sent to the central ECG lab. The investigator will judge data adoption and send the information which ECGs were adopted to the central ECG lab.

Unscheduled ECGs (for safety reasons) will be transferred to the central ECG lab but will not be included into the statistical analysis of interval lengths.

Data transfer from the central ECG lab to the sponsor is described in the ECG data transfer agreement (refer to TMF).

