Previous and concomitant therapies will be presented per treatment group without consideration of time intervals and treatment periods.

Proprietary confidential information © 2018 Boehringer Ingelheim International GmbH or one or more of its affiliated companies

Laboratory data will be compared to their reference ranges. Values outside the reference range as well as possibly clinically significant values will be highlighted in the listings. Additionally, differences from baseline will be evaluated.

Vital signs or other safety-relevant data will be assessed with regard to possible on-treatment changes from baseline.

The ECG variables QT, HR, QTcF, QTcB, PR, QRS, and RR obtained from the centralised evaluation of 12-lead ECG recordings will be the basis for the derivation of quantitative and categorical ECG endpoints. These endpoints and their analyses will be described in the TSAP.

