## **6.6 HANDLING OF MISSING DATA AND OUTLIERS**

Handling of missing data and outliers will be performed as described in the CTP, Section 7.5.

The only exceptions where imputation might be necessary for safety evaluation are AE dates. Missing or incomplete AE dates are imputed according to BI standards (see 001-MCG-156\_RD-01 (4)).

Missing data and outliers of PK data are handled according to BI standards (see 001-MCS-36-472\_RD-01) ([5](#)).

If single cardiac cycles of an ECG (out of the generally four) are missing, the arithmetic mean for this single ECG will be computed with the reduced (1, 2 or 3) number of cardiac cycles.

If replicate ECG recordings are missing, the arithmetic means per time point will be computed with the reduced number (1 or 2) of recordings.

For the classification of the on treatment QTc/QT intervals into “no new onset” / “new onset” categories, a missing value is obtained only in case that

- (i) all on treatment values are missing and
- (ii) the baseline value is less than or equal to 500 msec, or missing.

If condition (i) is fulfilled but the baseline value is greater than 500 msec, this case will be categorized as ‘no new onset’. If baseline is missing and the maximum on treatment QTc interval is greater than 450 msec (or 500 msec for QT interval, respectively), this is classified as a ‘new onset’ in the respective category. If baseline is missing and the maximum QTc interval is less than or equal to 450 msec (or 500 msec for QT interval, respectively), this will be categorized as ‘no new onset’. If baseline is missing, a QTc/QT interval > 500 msec at any time on treatment will be a notable finding.

For placebo subjects, the missing plasma concentration values will be replaced by 0 for the exposure-response analyses. For subjects on active drug, missing plasma concentration values with ‘BLQ’ in the comment field will be replaced by ½ LLOQ.

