## 6.7 BASELINE, TIME WINDOWS AND CALCULATED VISITS

The baseline value is defined as the last measurement before administration of BI 730357 or Placebo.

**Section 6.1 of the CTP:** *Exact times of measurements outside the permitted time windows will be documented. The acceptable time windows for screening and end of study examination are given in the CTP Flow Chart.*

*Study measurements and assessments scheduled to occur ‘before’ trial medication administration on Day 1 are to be performed and completed within a 3 hours-period prior to the trial drug administration (including blank values for PK).*

*The tolerance for drug administration will be ± 1 minute on Days 1.*

*The acceptable deviation on Day 1 from the scheduled time for vital signs and ECG will be -15 minutes for the first 4 hours after the drug administration and - 30 minutes thereafter. After Day 2, vital signs and ECG will be ± 30 minutes from the scheduled time. Blood sampling for safety laboratory tests will be ± 30 minutes for the first 24 hours after trial drug*

*administration. Urine sampling for safety laboratory tests will be -3 hours on Day 2 (24 hours after trial drug administration).*

*Procedures on Days 4, 5 and 8 to be performed within  $\pm 3$  hours from planned time.*

Adherence to time windows will be checked via the consistency check listings at the RPM/DBLM.

Unscheduled measurements of laboratory data or vital signs will be assumed to be repeat measurements of the most recent scheduled measurement (e.g. for follow-up or confirmation of a particular value). Therefore, unscheduled measurements will be assigned to the planned time point of the previous scheduled measurement.

There will be a centralised evaluation of the 12-lead ECG recordings at the time points and for the ECG recordings specified in the [Table 6.7: 1](#) below:

Table 6.7: 1 Time schedule of 12-lead ECG recordings

Visit	Day	Planned time [hh:mm] (relative to drug administration)	Study phase	Central evaluation
1	-28 to -2		Screening	NA
2	1	-03:00	Baseline	all 3 single ECGs of the triplicate
		00:30		first single ECG of the triplicate
		01:00		first single ECG of the triplicate
		02:00		first single ECG of the triplicate
		03:00		first single ECG of the triplicate
		04:00		first single ECG of the triplicate
		06:00		first single ECG of the triplicate
		08:00		first single ECG of the triplicate
		12:00		first single ECG of the triplicate
	2	24:00		single ECG
		34:00		single ECG
	3	48:00		single ECG

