#### **Categorical endpoints**

For the categorical endpoints, frequency tables will be provided.

For all subjects with any notable finding in ECG intervals, a separate listing will be created as end-of-text display (based on the same display template as in Appendix 16.2), and the corresponding time profiles will be shown.

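### As written, a QT/QTc threshold exceedance seen only on an unscheduled safety ECG stays out of the new-onset tables and possibly out of the notable-finding listing, so ECG outlier counts can only be understated

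*Protocol*

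**What the plan says.** Protocol 5.2.4.1, Recording: "Additional (unscheduled) ECGs may be collected at the discretion of the investigator for safety reasons". It then fixes their place in the schedule: "These ECGs are assigned to the prior scheduled time point".

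Protocol 5.2.4.1, Data transfer, sends these unscheduled ECGs to the central ECG lab but says that they "will not be included into the statistical analysis of interval lengths". The sentence makes no exception for categorical endpoints.

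Protocol 7.3.4 says that the ECG variables "obtained from the centralised evaluation of 12-lead ECG recordings will be the basis for the derivation of quantitative and categorical ECG endpoints", and leaves the definition of those endpoints to the SAP.

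SAP 6.7 states: "There will be a centralised evaluation of the 12-lead ECG recordings at the time points and for the ECG recordings specified in the" table that follows. That table (Table 6.7: 1) lists planned times only. The rule in SAP 6.7 that moves unscheduled measurements to the previous planned time names laboratory data and vital signs, not ECGs.

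SAP 6.6 says, for a subject without a baseline, that "a QTc/QT interval > 500 msec at any time on treatment will be a notable finding". SAP 7.8.4 plans frequency tables for the categorical endpoints and adds: "For all subjects with any notable finding in ECG intervals, a separate listing will be created".

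**The concern.** Leaving discretionary ECGs out is sensible for means by time point and for concentration-ECG pairs, where an extra reading would distort a planned-time summary or lack a matching plasma sample. A threshold count is different. It asks whether a subject ever crossed a fixed limit, and dropping readings can never raise the answer. The readings dropped here are those taken because an investigator had a safety reason to look, so they are not missing at random with respect to the outcome being counted.

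What is at stake is the completeness of the new-onset tables and the notable-finding listing. In a trial with six active subjects per dose, these displays are read subject by subject.

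**Working it through.** The plan gives no figure to reproduce, so the check sets the rules side by side and then sizes one omitted subject.

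**1. Do unscheduled ECGs reach the categorical endpoints?**
- Protocol 5.2.4.1 (Data transfer) excludes them from the interval analysis.
- Protocol 7.3.4 bases the quantitative and the categorical endpoints on the central evaluation.
- SAP Table 6.7: 1 specifies that evaluation as the baseline triplicate plus 12 planned post-dose times (0:30, 1, 2, 3, 4, 6, 8, 12, 24, 34, 48 and 72 h).
- The unscheduled-measurement rule in SAP 6.7 does not cover ECGs.

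On the visible text, they do not.

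**2. Direction of the effect.** Let S be a subject's scheduled on-treatment values and U the unscheduled ones. Then max(S) ≤ max(S and U together). For any fixed limit, using S alone can turn an exceedance into a non-exceedance and never the reverse. This assumes that the endpoint is a threshold on the highest on-treatment value. SAP 6.6 points that way: the new-onset class is set to missing only when all on-treatment values are missing and baseline is missing or at most 500 ms. The baseline is the mean of the pre-dose triplicate (SAP 6.7), so unscheduled post-dose ECGs leave it unchanged.

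**3. Comparison with laboratory data.** SAP 6.7 keeps unscheduled laboratory values at the previous planned time, and SAP 7.8.2 summarises the worst value there. The protocol also assigns unscheduled ECGs to the prior planned time, but that has little analytical use if they are then excluded.

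**4. Are they centrally read at all?** The Evaluation paragraph of protocol 5.2.4.1 covers all 12-lead ECGs up to 72 h. Table 6.7: 1 covers planned recordings only. The two do not agree for unscheduled ECGs.

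**5. Where an unscheduled ECG could be the only 12-lead reading.** Gaps between planned centrally read ECGs after 12 h:
- 24 − 12 = 12 h
- 34 − 24 = 10 h
- 48 − 34 = 14 h
- 72 − 48 = 24 h

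The on-treatment phase runs to 7 days (SAP 6.1), that is 168 h, so a further 168 − 72 = 96 h has no centrally evaluated ECG.

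**6. Size of one omission (illustration).** Assume one active subject with a baseline at or below 450 ms, a scheduled maximum QTc of 445 ms and an unscheduled value of 505 ms. Active subjects: 3 × 6 = 18. Exact 95% Clopper-Pearson intervals:

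| Count | Excluded (as written) | Included |
|---|---|---|
| Dose group | 0/6 = 0% (0 to 45.9%) | 1/6 = 16.7% (0.4 to 64.1%) |
| All BI 730357 | 0/18 = 0% (0 to 18.5%) | 1/18 = 5.6% (0.1 to 27.3%) |

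The upper limit for 0/n is 1 − 0.025^(1/n), which gives 0.459 for n = 6 and 0.185 for n = 18.

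**The case against.** **The governing definitions are not visible.** SAP 6.6 and 7.8.4 use the terms new onset and notable finding without defining them. The SAP also cites sections (7.6, 9.1, 9.3) that are not in the available text. A reader might infer that the SAP contains no rule for these ECGs at all; only the visible text can be judged. This stands as a limit. It does not remove the point, because an exception in the unseen text would contradict the protocol sentence and would still need reconciling.

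**The SAP 6.6 wording is conditional.** A reader might infer that SAP 6.6 defines the endpoints generally by the highest value, or by any value, on treatment. Those sentences apply only when baseline is missing, so the general definition is inferred, not shown.

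**The exclusion may be narrower than it looks.** The protocol sentence concerns statistical analysis, and SAP 7.8.4 treats individual listings separately from frequency tables. An unscheduled value could therefore still appear in a listing. This is why the listing effect is put only as possible.

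**Subject safety is covered elsewhere.** A reader might infer that a QT signal would be lost or that the primary endpoint is biased. The documents do not support this. Cardiac safety during the trial rests on local QTcF values, with early central assessment in doubtful cases (protocol 5.2.4.1). Clinically relevant findings become adverse events whether read locally or centrally, and the primary endpoint counts subjects with drug-related adverse events. The adverse event route does not replace a fixed-threshold table, however, because it depends on the investigator's judgement of relevance.

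**A fixed schedule protects comparability.** More readings raise a subject's expected maximum, and protocol 3.2 acknowledges possible observer bias because dose level is known to investigators. Active or placebo status is blinded to them, and placebo outliers are excluded by the same rule, so the direction is certain for counts but not for the contrast with placebo. This stands, and it is a reason to show both counts.

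**Conclusion.** The point holds for the ECG outlier displays only. Followed as written, the plan leaves a threshold exceedance seen only on an unscheduled on-treatment ECG out of the new-onset frequency tables, and possibly out of the notable-finding listing. The error can only lower the counts.

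The frequency of such cases cannot be estimated from the documents. The 0/6 versus 1/6 comparison shows what one subject would do, not what is expected; protocol 1.2.5 reports no clinically relevant ECG changes in the preliminary data of the multiple-dose trial.

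The conclusion rests on two assumptions: that the unseen endpoint definitions contain no exception for unscheduled ECGs, and that the categorical endpoints summarise the highest on-treatment value.

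**What to change.** - In protocol 5.2.4.1 and SAP 6.7 and 7.8.4, limit the exclusion of unscheduled safety ECGs to by-time descriptive statistics and the exposure-response pairs.
- Count unscheduled on-treatment ECGs towards the new-onset categories, the notable-finding flags and the end-of-text listing. Mark them as unscheduled, and show the counts with and without them.
- Reconcile the Evaluation paragraph of protocol 5.2.4.1 with SAP Table 6.7: 1, so that it is clear whether transferred unscheduled ECGs are centrally read, and say what applies between 72 h and the end of the 7-day on-treatment phase.

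The cost is a short text change in both documents and a small programming change. The recordings already go to the central lab. If Table 6.7: 1 is meant to limit what is read, the unscheduled ECGs also need reading, and the documents give no number for these. The remaining downside is that subjects with safety ECGs contribute more readings and that dose level is known to investigators, so the two counts should be read together.
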